## 1.2 BACKGROUND ON RO7020531

RO7020531, an oral double prodrug of the TLR7-specific agonist, RO7011785, is being developed for the treatment of CHB patients. A prodrug approach was chosen for oral delivery of the TLR7 agonist RO7011785 in order to improve bioavailability and

potentially limit TLR7 activation in the gastrointestinal (GI) tract, which may be associated with GI intolerance. Non-clinical studies with RO7020531 suggest that it is rapidly converted to the active metabolite RO7011785. Data from in vivo studies with RO7020531 and in vitro studies with RO7011785 support immune activation as the mechanism of action. A clinical study (NP39305) of RO7020531 exploring safety, PK and PD effects is ongoing (see Section [1.2.2](#)).

See the RO7020531 Investigator's Brochure ([RO7020531 IB](#)) for details on non-clinical studies.

### **1.2.1 Previous Non-Clinical Studies**

RO7011785 showed in vitro potency to activate TLR7 and triggered downstream TLR7-mediated nuclear factor-kappa B (NF- $\kappa$ B) signaling in an engineered HEK293 reporter cell line expressing human TLR7. RO7011785 was shown to be a selective hTLR7 agonist with less potency to activate hTLR8 in vitro. Ex vivo stimulation of human peripheral blood mononuclear cells (PBMCs) from healthy donors by RO7011785 resulted in dose-dependent induction of various cytokines and chemokines, including IFN- $\alpha$ , tumor necrosis factor- $\alpha$  (TNF- $\alpha$ ), interleukin-6 (IL-6), and IFN gamma-inducible protein 10 (IP-10).

In an HBV mouse model, C57BL/6 mice were injected with recombinant adeno-associated virus harboring 1.3 copies of the HBV genome, and demonstrated high levels of HBV viral makers including HBV DNA, HBsAg, and HBeAg. Oral administration of RO7020531, once a week (QW) or every other day (QOD) for 6 weeks, proved to have in vivo anti-HBV activity in this mouse model, i.e., clear reduction in HBV DNA and HBsAg (by more than 1 log after the 42-day treatment period). With the same administration frequency, higher doses resulted in faster and greater reduction in HBV DNA and HBsAg. With the same dose of 100 mg/kg, QOD administration resulted in greater viral reduction on Day 42 than QW administration. In addition, RO7020531 induced interferon-stimulated gene expression in peripheral whole blood in this mouse model.

RO7020531 showed high oral bioavailability and rapid conversion to the active moiety, RO7011785. RO7011785 exhibited a relatively short half-life ( $t_{1/2}$ ) of 1.51 hours in rats and 2.12 hours in monkeys, moderate systemic clearance (CL) of ~50% liver blood flow in rats, and CL of approximately 30% liver blood flow in monkeys. RO7011785 had a moderate volume of distribution ( $V_{ss}$ ) in the range of body water or slightly higher for both rats and monkeys. Differences in metabolite exposure were noted between species, although RO7011785 was the predominant metabolite in both rats and monkeys, confirming good conversion to active drug.

Conversion of RO7020531 to the active form RO7011785 was observed in animal and human hepatocytes, with both the ester hydrolysis and aldehyde oxidase-mediated pathways active. The relative strength of the oxidase versus esterase pathways varied

between species and influenced the concentrations of the different intermediate prodrugs: RO7033805 was the predominant intermediate for cynomolgus monkey, whereas RO7018822 was the predominant intermediate for mouse, rat, and human.

RO7020531 was found to be a good substrate of multidrug resistance protein 1 (MDR1; P-glycoprotein), with a high apparent membrane permeability. Therefore, *in vivo* drug-drug interactions due to co-administration with MDR1 inhibitors cannot be excluded. However, interactions of strong MDR1 inhibitors with the absorption of RO7020531 are considered unlikely due to the high permeability, high solubility, and high oral bioavailability of RO7020531, which makes it unlikely that MDR1 plays a major role in RO7020531 trans-intestinal absorption *in vivo*.

RO7011785 can be directly glucuronidated by UDP-glucuronosyltransferase 1A1 (UGT1A1); thus, drug-drug interactions with UGT1A1 inhibitors cannot be excluded. Drug-drug interaction potential was low, as determined *in vitro* with cytochrome P450 (CYP) enzymes and with transporters (organic anion transporting polypeptide 1B1 [OATP1B1], OATP1B3, organic anion transporter 1 [OAT1], OAT3, and breast cancer resistance protein [BCRP]). Therefore, the interactions with CYPs and substrates for hepatic uptake transporters and kidney transporters (for example NUCs) *in vivo* are unlikely.

Repeat-dose toxicity studies with treatment duration of up to 13 weeks have been performed with RO7020531 in rats and monkeys. The effects observed were considered to be consistent with exaggerated pharmacology, i.e., TLR7 agonism leading to the intended immune/cytokine stimulation and subsequent tolerability or pro-inflammatory findings. QOD and QW dosing regimens were investigated in Good Laboratory Practice (GLP) toxicology studies. The no-observed-adverse-effect level (NOAEL) for the 13-week rat toxicology study was 3 mg/kg QOD (area under the concentration–time curve for males and females  $AUC\ M/F = 186/503\ h \cdot ng/mL$ ) and 30 mg/kg QW ( $AUC\ M/F = 2950/4660\ h \cdot ng/mL$ ). The NOAEL for the 13-week monkey toxicology study was 3 mg/kg QOD ( $AUC\ M/F = 858/706\ h \cdot ng/mL$ ) and 10 mg/kg QW ( $AUC\ M/F = 3340/2960\ h \cdot ng/mL$ ).

Neither the double prodrug RO7020531, nor its metabolites RO7011785 and RO7018822, significantly affected potassium channels in the *in vitro* human ether-à-go-go-related gene (hERG) assay. Dosing at  $\geq 3\ mg/kg$  in monkeys caused reversible heart rate (HR) increase (with decreased RR interval and shortened QT and/or heart-rate corrected QT [QTc] interval), non-adverse increase in PR interval and increase in body temperature. There were no RO7020531-related effects on respiratory or central nervous system function in rats up to the highest dose tested (300 mg/kg).

No genotoxic potential was observed for RO7020531 in the Ames test, nor in the *in vitro* and *in vivo* micronucleus test. No evidence of teratogenicity or embryo-fetal toxicity was observed in definitive (GLP) embryo-fetal toxicity studies in rats (up to 150 mg/kg/day) or

rabbits (up to 100 mg/kg/day), other than increased incidences of non-adverse fetal skeletal variations. In a definitive (GLP) fertility study in rats, no adverse effects of RO7011785 on mating performance, fertility, or early embryonic development were noted (up to 300 mg/kg, every other day [QOD]), despite slightly reduced body weight gain. See the [RO7020531 Investigator's Brochure](#) for details on the properties of RO7020531 and RO7011785.

### **1.2.2 Previous Clinical Studies**

A global entry-into-human (EIH) study (NP39305) is ongoing, where RO7020531 is being evaluated in healthy volunteers in single ascending doses (SAD) and multiple ascending doses (MAD) and subsequently will be evaluated in virologically suppressed CHB patients.

*As of 1 October, 2017, 80 healthy volunteers (HVs; 64 males and 16 females) have been dosed with RO7020531/placebo in eight SAD cohorts. All dose levels (3 mg, 10 mg, 20 mg, 40 mg, 60 mg, 100 mg, 140 mg and 170 mg) were considered safe and well tolerated. There had been few adverse events (AEs) per cohort, all were reported as of mild intensity, and only three subjects (two in the second cohort [10mg] and one in the 170 mg cohort) had AEs that were considered "related" to study drug. No serious adverse events (SAEs) or discontinuations due to AEs had been reported; and there were no dose related trends in nature, incidence or severity of AEs. In addition, there have been no clinically significant changes (or trends) in ECG parameters, vital signs, or laboratory safety test results in any subjects.*

*Exposure (AUC0-inf) of the main active metabolite, RO7011785, increased proportionally with dose and was consistent with values predicted for humans from preclinical pharmacokinetics (PK) models. PD biomarkers did not have significant changes after single doses up to 60 mg in SAD Cohorts 1-5. Three out of eight subjects in SAD Cohort 6 who received a single RO7020531 dose of 100 mg exhibited changes in interferon alpha indicative of TLR7 activation. Two of these subjects exhibited increased activity for IP10 and neopterin. The fraction of subjects responding as well as the amplitude of the response increased at the 140 mg dose. Changes in mRNA levels for ISG15, OAS-1, MX1 and TLR7 initially found at the 100 mg dose were amplified at the 140 mg dose.*

## **1.3 STUDY RATIONALE AND BENEFIT–RISK ASSESSMENT**

### **1.3.1 Study Rationale**

Study YP39553, is a Phase I study to assess the safety, tolerability, pharmacokinetics (PK) and pharmacodynamics (PD) of RO7020531 following oral administration of SAD and MAD in Chinese healthy subjects.

Safety and tolerability of ascending doses of RO7020531 will be the primary endpoint in this study. In addition, PK and PD measured via the appearance of select biomarkers

indicating activation of TLR7 and/or TLR8, will be evaluated. These biomarkers will be evaluated for each cohort in the SAD and will be used in a decision to initiate the MAD.

The MAD part is designed to dose subjects with RO7020531 using a QOD regimen that will proceed for two weeks. Previous clinical and non-clinical data with another TLR7 agonist, RO6864018, have shown that the QOD dose schedule provides additional priming of the TLR7 response and is thought to be a dose regimen that may optimize the benefit-risk ratio for HBV treatment.

Evidence for TLR activation in the SAD and MAD studies will be provided by measuring post-dose changes in *selected* biomarkers including *the protein and metabolite markers IFN- $\alpha$ , IP-10, TNF- $\alpha$ , IL-6, IL-10, IL-12p40 and neopterin and markers of transcriptional responses (ISG15, OAS-1, MX1 and TLR7)*, known to be stimulated by activation of TLR7 and/or TLR8.

### **1.3.2      Benefit-Risk Assessment**

The evaluation of potential risks of treatment and specific tests, observations, and precautions required for clinical studies with RO7020531 are based on information from non-clinical toxicology and safety pharmacology studies, and on information/in house experience from clinical studies with other TLR7 agonists ([Gane 2015](#), [Grippo, 2016](#)). Furthermore, information from clinical data collected from the global EIH Study NP39305 will be available prior to starting to dose subjects in this study. The doses/exposures to be explored in this study should be considered safe and with acceptable tolerability based on study NP39305.

Safety and tolerability will be carefully assessed, and healthy volunteers will be closely monitored. The [RO7020531 IB](#) summarizes potential risks and key risk management activities to consider when dosing this compound.

As for all early clinical studies in healthy volunteers, there is no direct benefit to the subjects participating in this study. However, this study will be essential in the development of a new treatment for chronic HBV infection, and for selecting the most appropriate dose for a study in HBV-infected patients.

## **2.            OBJECTIVES**

### **2.1            PRIMARY OBJECTIVES**

The primary objective of this study is:

- To assess the safety and tolerability of single and multiple ascending doses of oral RO7020531 in Chinese healthy subjects.

## **2.2 SECONDARY OBJECTIVES**

The secondary objectives for this study are as follows:

- To investigate the plasma PK of RO7020531 and the main active metabolite, RO7011785, following single and multiple ascending doses of RO7020531 in Chinese healthy subjects. Additional metabolites may be measured, including RO7018822 and RO7033805.
- To investigate the urine PK of RO7020531 (if detectable) and the main active metabolite, RO7011785, in urine samples of Chinese healthy subjects after single ascending oral doses of RO7020531. Additional metabolites may be measured in urine, including RO7018822 and RO7033805.
- To investigate the effect of RO7020531 on PD parameters following single or multiple oral doses administered QOD in Chinese healthy subjects.

## **3. STUDY DESIGN**

This study will be a randomized, Sponsor-open, Investigator/subject-blinded, placebo-controlled, SAD and MAD study to evaluate the safety, tolerability, PK and PD of RO7020531 and metabolites following oral administration to Chinese healthy subjects. PK, PD, safety and tolerability data collected in the SAD part of this study will be used to determine doses at which to initiate the MAD part of the study. A QOD dosing regimen will be evaluated in the MAD portion of this study.

### **3.1 DESCRIPTION OF STUDY**

#### **3.1.1 Overview of Study Design**

For both SAD and MAD parts of the study, each cohort will enroll ten subjects, with eight subjects randomly assigned to RO7020531 and two subjects randomly assigned to placebo ([Table 1](#)). Each cohort will include a minimum of two females, with at least one female receiving active drug. All single and multiple doses will be administered in the fasted state.

**Table 1 Study Cohorts**

Cohort	Stage	Dose (mg) a	Total Doses Administered	Route	Planned Number of Healthy Volunteers	
					Active Drug	Placebo
1	SAD	40	1	PO	8	2
2	SAD	100	1	PO	8	2
3	SAD	140	1	PO	8	2
4	SAD	170 b	1	PO	8	2
1	MAD	TBD	7 QOD	PO	8	2
2	MAD	TBD	7 QOD	PO	8	2

SAD = single ascending doses; MAD = multiple ascending doses; TBD = to be determined; QOD = every other day.

- a. Proposed doses, which will be refined based on PK, safety and tolerability found in the global EIH study NP39305 *and/or in the previous cohorts in the current study YP39553*;
- b. Optional cohort.

Additional cohorts may be explored in the SAD and MAD part as required.

### 3.1.1.1 Single Ascending Dose Study

For dose escalation, subjects will be sequentially enrolled into approximately four to six dose cohorts that may range between 40 mg and 170 mg, the maximum dose proposed in the global EIH study, NP39305. *Based on the newly available data in NP39305 indicating very good safety and tolerability with single RO7020531 doses up to 170 mg and PD effects documented only with doses  $\geq 100$  mg, the starting dose in this study was selected to be 40 mg, which is expected to avoid very low doses/exposures that may not produce pharmacodynamic effects, while ensuring appropriate safety margins expected with the first dose (See Section 3.2.1).*

The anticipated ascending dose scheme in the SAD cohorts is 40 mg, 100 mg 140 mg and 170 mg. Additional cohorts may be added within a dose range between 10 mg and 170 mg (Figure 1). As an additional safety precaution in this study, the subjects participating in each single dose cohort will be dosed according to a sentinel dosing design. Initially, two subjects will be dosed: one subject with RO7020531 and one subject with placebo. If the safety and tolerability results from the first 24 hours following dosing for the initial subjects are acceptable to the Investigator, the remaining subjects of each cohort may be dosed soon after.

As described below, PK/PD and safety data from the SAD cohorts will be utilized to select the starting dose for the MAD. If only three cohorts are required to choose a starting dose for the MAD, then further cohorts may not be evaluated. The final doses chosen for evaluation may be modified based on data collected in Study NP39305 and/or from the previous cohorts in the current study. If adequate safety and tolerability are documented in a dosing cohort, further dose progression may be explored but not

until a consensus agreement is reached between the Sponsor and the Investigator; the Ethics Committee will be informed. RO7020531 doses planned for this study in Chinese healthy volunteers will not be evaluated if they are expected to result in RO7011785 exposures which are not found to be safe and tolerable in the global EIH study. In addition, doses will not be escalated in both the SAD and MAD if stopping rules have been met (see Section 3.1.3). Safety and tolerability at each dose level will determine eligibility for dose escalation. Measurement of PK and select PD markers will be made with each cohort and, upon availability, will be utilized along with safety data to determine the first dose with which to initiate the MAD. The MAD part of this study may be initiated before the SAD part is completed. Therefore, both SAD and MAD parts of this study may run in parallel.

In the SAD cohorts, subjects will be screened up to 28 days before randomization and asked to remain in the unit from Day – 2 until Day 3 with dosing occurring on Day 1. After being discharged on Day 3, subjects will return for an outpatient visit on Day 5 and a follow-up visit on Day 8. All subjects will have a follow-up phone call 28 days after the study drug administration. Subjects will be asked to report any AEs that occur during this period.

### **3.1.1.2      Multiple Ascending Dose Study**

The trigger to start the first cohort in the MAD includes documentation of adequate safety and tolerability in the SAD cohorts and evidence of PD effects. For a given dose evaluated in the SAD, evidence in at least two subjects exhibiting responses above placebo-defined baseline for select PD biomarkers, including *the protein and metabolite markers IFN- $\alpha$ , IP-10, TNF- $\alpha$ , IL-6, IL-10, IL-12p40 and neopterin and markers of transcriptional responses (ISG15, OAS-1, MX1 and TLR7)*, should be demonstrated. If the next dose in the SAD has been considered safe, then the previous dose demonstrating TLR-associated PD activity will be considered as the starting dose for the MAD. In addition, the starting dose/exposure in the MAD part of this study should have been considered safe in the global EIH study (NP39305). Only doses covered by the dose range evaluated in the SAD part will be used in the MAD, and two to three dose levels will be evaluated (Figure 1).

[figure not shown]
Once criteria have been reached to determine an initial dose for MAD, subjects will be screened up to 28 days before enrollment into the MAD part of this study. They will be asked to remain in the unit from Day -2 until Day 14 with QOD dosing initiated on Day 1. In total, 7 QOD doses will be administered with the last dose given on Day 13. Subjects will be discharged on Day 14. After completing 7 QOD doses, each subject in the MAD cohorts will return for an outpatient follow-up visit 7 days after the last dose. All subjects will have a follow-up phone call 28 days after their last dose. Subjects will be asked to report any AEs that occur during this period.

Upon safety review of the MAD cohort(s) data, dose escalation will proceed in the MAD part of this study. The maximum dose investigated in MAD will not exceed doses

evaluated in the SAD part of this study nor will it exceed doses and exposures considered to be safe and with acceptable tolerability in the global EIH study.

Based on the PK, PD and safety evaluation of the previous dose cohorts, additional cohorts of subjects may be enrolled at higher or lower dose levels, or at a dose level already tested.

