### RATIONALE

Protocol YP39553 has been amended to incorporate the following changes:

- **The dose sequence in the single ascending dose (SAD) portion of the study has been modified based on availability of new safety, pharmacokinetic, and pharmacodynamic (PD) data in the ongoing entry-in-human (EIH) study NP39305 (Sections 3.1.1, 3.1.1.1, 3.1.2, 3.2.1, 4.4.1.1, and 4.4.2.1).**

The newly available data in NP39305 indicated very good safety and tolerability with single RO7020531 doses up to 170 mg and PD effects documented only from doses  $\geq$  100 mg. The starting dose in this study was modified from 10 mg to 40 mg. This is expected to avoid very low doses/exposures that may not produce PD effects, while ensuring appropriate safety margins expected with the first dose. A planned dose escalation sequence of the SAD cohorts is anticipated to be 40 mg, 100 mg, and 140 mg and 170 mg. This sequence is based on the global EIH study results and ranges from one inactive dose through safe doses found to have PD activity.

- **The protocol text and reference to the Investigator's Brochure have been updated to incorporate new clinical safety, pharmacokinetic, and pharmacodynamic information from the ongoing study NP39305 (Sections 1.2.1, 1.2.2, and 10).**
- **Pharmacodynamic outcome measures (e.g., ISG15, OAS-1, MX1 and TLR7) have been added to evaluate markers of transcriptional responses to improve dose selection for the MAD part of the study (Section 1.3.1, 3.1.1.2, 3.2.4, 3.3.3, and 4.6.1.7, and 6.7 and Appendices 1-4).**

The determination of TLR7 response by measuring various markers including ISG15, OAS-1, MX1 and TLR7 at the transcriptional level (mRNA determinations) has been shown to be a sensitive method to demonstrate TLR7- dependent response in the NP39305 study. In that study, higher level of response was noted for changes in the transcriptional markers than for the cytokines or neopterin at the 100 mg dose. This enabled clear determination of suitable doses for evaluation in the MAD portion of that study and it is anticipated will better enable dose selection in YP39553.

The PD activity in the SAD part, including changes in the expression of the interferon response genes, will be used to help choose the starting dose in the MAD part of the study.

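### Does the undefined PD responder in the trigger for the multiple-dose part (Section 3.1.1.2) leave the choice of starting dose to chance?

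*Combined protocol and SAP*

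**What the plan says.** Section 3.1.1.2 makes the start of the MAD part depend on adequate safety and tolerability in the SAD cohorts and on PD effects. The PD element is "evidence in at least two subjects exhibiting responses above placebo-defined baseline for select PD biomarkers". Eleven markers are named: seven protein or metabolite markers and four transcripts. Once the next SAD dose is considered safe, "the previous dose demonstrating TLR-associated PD activity will be considered as the starting dose for the MAD".

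Each cohort has "eight subjects randomly assigned to RO7020531 and two subjects randomly assigned to placebo" (Section 3.1.1). Section 3.1.1.1 adds that "The MAD part of this study may be initiated before the SAD part is completed", and also: "If only three cohorts are required to choose a starting dose for the MAD, then further cohorts may not be evaluated". The Version 2 rationale says that the PD measures "have been added to evaluate markers of transcriptional responses to improve dose selection for the MAD part of the study".

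The protocol gives no cut-off, baseline sample, post-dose time or placebo pool for a response, and does not say whether both subjects must respond on the same marker. Section 6.7 is descriptive and exploratory, and Section 6.9 plans no interim analysis. Section 3.2.1 mentions predefined criteria for TLR7 marker activity in NP39305, but does not state them or adopt them for this trial.

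**The concern.** A count of two has a known error rate only when the event being counted is defined. Here the reference could be the placebo mean, the highest placebo value, or a mean plus some number of standard deviations. If it comes from SAD placebo alone, it rests on four subjects after two cohorts and six after three, and an SD from so few is unstable. The sponsor's teams are unblinded (Section 4.3), so a cut-off left open could be settled after the results by arm are known.

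At stake is the MAD starting dose. In NP39305, "PD biomarkers did not have significant changes after single doses up to 60 mg in SAD Cohorts 1-5", yet the first cohort here receives 40 mg. If two of its eight active subjects cross the line by chance and 100 mg is then judged safe, the text makes 40 mg a candidate. A MAD cohort could then be spent at a dose with little PD activity, although the transcripts were added to sharpen this very choice.

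**Working it through.** **Inputs.** Eight active and two placebo subjects per cohort (Section 3.1.1 and Table 1); at least two responders (Section 3.1.1.2); SAD doses of 40, 100, 140 and 170 mg (Table 1). The PD trigger has no stated error rate. The one operating characteristic given, a 90% chance of seeing at least one AE of 25% incidence (Section 6.1), reproduces: 1 − 0.75^8 = 0.8999.

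**Chance rates, one marker, no drug effect, m placebo subjects.**
- Above the highest placebo value, any continuous distribution: P = 8/(8+m) × 7/(7+m). For m = 4, 56/132 = 42.4%. For m = 6, 56/182 = 30.8%.
- Above placebo mean + 2 SD (simulation, normal data): 17.2% for m = 4, 11.7% for m = 6.
- Above placebo mean + 3 SD (same): 7.1% and 3.1%.

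These are illustrations and do not bound the possible readings. With m = 4, exceeding the placebo mean alone gives about 89%, and a one-sided 97.5% prediction limit gives 4.6%. Log-normal data (log-SD 0.5 to 1) raise the mean + 3 SD figure to 15%–22%. If two subjects crossing on the same one of any of the eleven markers were enough (correlation 0.5), the rate runs from 44% (mean + 3 SD) to 93% (highest placebo). The rate is thus set by the definition assumed, and none of these definitions is in the protocol.

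**Where a no-effect rate applies.**
- After 40 and 100 mg, the previous dose is 40 mg and the SAD placebo pool is 2 × 2 = 4. NP39305 suggests little or no activity at this dose, so the m = 4 rates are relevant.
- After 140 mg, the pool is 3 × 2 = 6, but the previous dose is 100 mg. Section 1.2.2 reports interferon-alpha changes in three of eight subjects at that dose, and transcript changes. The m = 6 rates assume no effect where the programme has already seen one.

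**What a fixed rule would buy.** One candidate uses the log change to 24 h on the four transcripts, with two subjects above placebo mean + 3 SD on the same transcript. The SD is the larger of the placebo SD and the SD of Day −1 to pre-dose changes in all subjects (Appendix 2 schedules both samples; 20 pairs after two cohorts, 30 after three).
- False triggers with four placebo subjects fall from 18%–25% (placebo SD alone) to 0.8%–1.0% (correlation 0.8 to 0).
- If post-dose changes are 25% more variable than drug-free ones, the rate is 3%–4%. If all four scheduled post-dose RNA times (2, 6, 12, 24 h) count, it is about 3%–5%, lower when both subjects must cross at the same time.
- Sensitivity matters at 100 mg, hence six placebo subjects. Assume each active subject responds with probability 3/8, on all four transcripts, correlation 0.5. At a 3-SD shift sensitivity falls from about 80% to 64%; at 2 SD, from 56% to 26%.
- Even perfect detection of true responders is capped at 1 − (5/8)^8 − 8 × (3/8) × (5/8)^7 = 86.5%.

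The 3/8 rate is borrowed from interferon-alpha, because the protocol gives no transcript response rate. The shifts are assumptions.

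**The case for a change.** The strongest case for a change is that a threshold of two means nothing until a response is defined. An unblinded team should not be free to set the line after seeing the data, and a few sentences would settle it at no cost in subjects or samples. Much of this stands: the definition is missing, and integrated judgement does not supply one. Recording the criteria before the first SAD PD review would be good practice.

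Three things weaken it as a demand on the plan. First, the sponsor is not starting from nothing. Section 3.2.1 shows that predefined marker criteria existed in NP39305, and the Version 2 rationale already describes the planned sequence as including one inactive dose. A chance crossing at 40 mg would be read against that. Second, the PD element does not decide alone. The candidate dose is only considered, Section 4.3 calls for PK, select PD, safety and tolerability to be weighed together, and Section 3.1.2 brings available PD data through 24 h into each SAD escalation, so 100 mg results may be in hand when 40 mg is discussed. Third, the detailed remedy is a trade-off. The transcripts have some support, since a "higher level of response was noted for changes in the transcriptional markers than for the cytokines or neopterin at the 100 mg dose". But fixing on four transcripts at 24 h sets aside IFN-alpha, IP-10 and neopterin, the only markers with subject-level response counts in Section 1.2.2. No text places the transcript peak at 24 h, and Section 3.2.1 says biomarker activity with a related agonist peaks as late as 48 h.

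**Conclusion.** No change is called for. Section 3.1.1.2 leaves out a definition that the sponsor's team can sensibly fill from the NP39305 criteria; it does not contain an error. With four placebo subjects and one marker, the illustrative chance rates of 7%, 17% and 42% are correct as arithmetic. The first two assume normal data, and all three assume that SAD placebo alone sets the reference. They are chances of meeting the PD element under assumed cut-offs, not chances of starting the MAD at an uninformative dose.

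The exposure is confined to 40 mg. An error there points to the lowest planned SAD dose, and Section 3.1.1.2 provides for escalation and for added cohorts at other doses. The likely cost is therefore time and one ten-subject cohort that says less than it might. The primary objective, safety and tolerability, is analysed descriptively and does not depend on the trigger. Against that modest cost, the stricter rule examined here loses about 16 percentage points of sensitivity at a 3-SD response (80% to 64%) and 30 at 2 SD (56% to 26%), so it is not a clear gain.
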